| 
Safety Stopping Criteria:
 | 
Enrollment will be stopped and the regulators will be notified if, at any time during the study, any of the following occur:
 
 • Death of a subject following administration of DTX301 • An event with an intensity of \geq Grade 3 (according to the Common Terminology Criteria for Adverse Events), but excluding hyperammonemic crises, develops following administration of DTX301 • Occurrence of a hepatic malignancy following administration of DTX301 
Abnormal clinically significant laboratory values (clinical chemistry, plasma ammonia, hematology, urinalysis, and coagulation panel) as assessed by the investigator will be considered AEs. Laboratory values that meet any of the above criteria will result in a pause in enrollment until the DMC reviews the data and provides a recommendation for subsequent study conduct.
 
Any event that meets any of the above criteria will be reported immediately and captured as an AE/SAE in the electronic case report form (eCRF), as appropriate. Enrollment and dosing will be temporarily suspended until the situation can be assessed and risks to the subjects mitigated. If an investigator reports an AE/SAE that meets any of the study stopping criteria, the DMC will meet on an ad hoc basis to review and assess the event. If study enrollment is suspended, all subjects who have been enrolled will remain in the study and will continue to be monitored through their completion or withdrawal from the study.
 
All AEs will be graded according to the most current version of the National Cancer Institute Common Terminology Criteria for Adverse Events.
 |
| 
Efficacy Assessments:
 | 
Efficacy assessments include:
 
The rate of ureagenesis, as measured by the generation of [¹³C]urea over 4 hours, will be determined by GCMS at Screening, on Day 1 and at 6, 12, 20, 24, and 52 weeks after IV administration of DTX301. During Screening, assessment of rate of ureagenesis may be repeated if discrepant with subject's clinical status and severity.
 
The change from Baseline (Day 0) in AUC₀₋₂₄ plasma ammonia at 6, 12, 24, and 52 weeks after IV administration of DTX301.
 |

| | |

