Eligible subjects will receive a single IV infusion of DTX301. Three subjects will be enrolled in Cohort 1 and a minimum of 2 to 3 subjects will be enrolled in each subsequent cohort; the number of subjects in each subsequent dosing cohort will be determined by subject results and availability of study product. Subjects in Cohorts 1 and 2 will be dosed at a minimum of 2 weeks (14 days) apart. The initial 3 subjects in Cohort 3 will be dosed at a minimum of 1 week apart (7 days). Additional subjects to Cohort 3 (Cohort Expansion) and subjects to Cohort 4 (Dosing Process Optimization) may be dosed less than 1 week apart. There will be a minimum of 12 weeks (84 days) followed by DMC review of a dosing cohort between the dosing of the last subject in one dosing cohort and the first subject in the next dosing cohort up to Cohort 3. Dosing of additional subjects as expansion of Cohort 3, and initiation of Cohort 4 (Dosing Process Optimization) may occur in parallel, following the DMC review of a minimum of 12 weeks of data from the initial 3 subjects in Cohort 3. Subjects may be assigned to either expansion of Cohort 3 or Cohort 4, with at least 1 male subject assigned to each. A continual reassessment method (CRM) will be used for dose finding to discover the OBD of DTX301 (Section 10.5.1). Cohort 4 is intended to dose at the OBD.

The proposed dosing interval of 14 days between subjects in the first and second dose cohorts, and 7 days between each of the first 3 subjects in Cohort 3, followed by a shorter dosing interval in the expansion of Cohort 3 and Cohort 4, is supported by the safety profile and lack of serious adverse

Protocol: 301OTC01

reactions reported in AAV-mediated gene transfer in human subjects, including those using AAV8 vector in a hemophilia B clinical study [Manno 2006; Nathwani 2011a; Nathwani 2014], and the ongoing safety review from this study, which includes DMC assessment [Diaz 2019; Ultragenyx Pharmaceutical, data on file]. Moreover, an ongoing Phase 1/2 clinical study in hemophilia B using AAV-mediated gene transfer at a starting dose of 5.0×10^{12} genome copies (GC)/kg (higher than the proposed DTX301 starting dose of 3.0×10^{12} GC/kg) at multiple European study sites is dosing subjects within a cohort at a minimum of only 1 day (24 hours) apart [uniQure 2014; Clinicaltrials.gov identifier: NCT02396342; EudraCT Number: 2013-005579-42].

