Subject safety will be closely monitored throughout the study, including assessment of hyperammonemic crises, assessment of metabolic and clinical stability, frequent monitoring of liver

Protocol: 301OTC01

enzymes and plasma ammonia levels, and inpatient observation following dosing and at multiple time points throughout the 52-week study duration.

After all subjects in Cohort 1 and Cohort 2, and the initial 3 subjects in Cohort 3 have completed Week 12, a data monitoring committee (DMC) will meet to review safety data (ie, AEs/SAEs, physical examination findings, vital sign measurements, electrocardiogram [ECG] results, and longitudinal clinical laboratory assessments [including assessment of liver function and plasma ammonia]) and provide a recommendation for progressing to the next dosing level, as applicable (Section 9.3), and enrollment of additional subjects to Cohort 3 (Cohort Expansion) and subjects to Cohort 4 (Dosing Process Optimization). If an investigator reports an AE/SAE that meets any of the study stopping criteria (Section 3.2.7), the DMC will meet on an ad hoc basis to review and assess the event. The DMC may, at any time, recommend modifying or pausing enrollment due to safety concerns based on these periodic data reviews. Additional DMC meetings may take place, as needed. The full scope of each review is outlined in the DMC charter.

Subjects will be followed for 52 weeks after dosing. After completion of this study, subjects will be asked to enroll in a 4-year extension study to evaluate the long-term (a total of 5 years after dosing) safety and efficacy of DTX301.

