3.2.7 Safety Stopping Criteria

Enrollment will be stopped, and the regulators will be notified if, at any time during the study, any of the following occur:

- Death of a subject following administration of DTX301
- An event with an intensity \geq Grade 3 (according to the Common Terminology Criteria for Adverse Events (CTCAE) [Section 9.1.3]), but excluding hyperammonemic crises (Section 3.2.6), develops following administration of DTX301
- Occurrence of a hepatic malignancy following administration of DTX301

Following DMC review when a stopping rule is met, if the decision is to restart enrollment, a substantial amendment will need to be approved by the regulatory authority.

Protocol: 301OTC01

Abnormal clinically significant laboratory values (clinical chemistry, plasma ammonia, hematology, urinalysis, and coagulation panel) as assessed by the investigator will be considered AEs. Laboratory values that meet any of the above criteria will result in a pause in enrollment until the DMC reviews the data and provide a recommendation for subsequent study conduct.

Any event that meets the above criteria will be reported immediately (within 24 hours) as outlined in Section 9.1.2.2 and the appropriate page(s) in the electronic case report form (eCRF) must be completed. Enrollment and dosing will be temporarily suspended until the situation can be assessed and risks to the subjects mitigated. The DMC will meet on an ad hoc basis if an investigator reports an AE/SAE that meets any of the study stopping criteria to review and assess the event. If study enrollment is suspended, all subjects who have been enrolled will remain in the study and will continue to be monitored through their completion or withdrawal from the study.

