9.3 Data Monitoring Committee

An independent DMC will be responsible for monitoring safety data from the study. The DMC will meet after all subjects in Cohort 1, all subjects in Cohort 2, and the initial 3 subjects in Cohort 3 have completed Week 12 of the study to review the safety data and to provide their recommendation for progressing to the next dosing cohort, or expansion of a dosing cohort. There will be no intra-cohort dose escalations. The DMC will also hold a meeting at completion of Week 12 for the first 3 subjects dosed in Cohort 4, and at the completion of Week 52 for all subjects. Additional DMC meetings may take place, as needed.

The DMC will meet on an ad hoc basis if an investigator reports an AE/SAE that meets any of the safety stopping criteria (Section 3.2.7). The DMC may, at any time, recommend modifying or pausing enrollment due to safety concerns based on these periodic data reviews. Following DMC review when a stopping rule is met, if the decision is to restart enrollment, a substantial amendment will need to be approved by the regulatory authority. The full scope of each review will be outlined in the DMC charter. The DMC will comprise at least either 3 independent medical professionals or 2 independent medical professionals and an independent biostatistician who are qualified to review the data and provide recommendations for progressing to the next dosing level and progressing to the next dosing cohort and cohort expansion. The DMC charter details the members' roles and responsibilities as part of the DMC as well as the process for each data review (ad hoc or scheduled).

10 Statistical and Analytical Plan

A statistical analysis plan (SAP) will be written and will provide a detailed description of the statistical methods and expand on the details provided in this protocol. Additional analyses may be added.

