10.5.1 Determination of the Optimal Biological Dose

The CRM uses the Bayesian method to model the probability of experiencing a DLT for each given dose in order to determine the next dose. A DLT is defined as any AE/SAE \geq Grade 3 that is considered related to DTX301 by the investigator [NCI CTCAE 2018].

The OBD is defined as the highest dose where the predicted probability of experiencing a DLT is less than the target toxicity level.

A high-level overview of the decision criteria to be used during dose finding are presented in Figure 10-1. Subjects (n=3) in the first cohort (Cohort 1) will be assigned to Dose 1.

Dose finding will continue in this manner until one of the following conditions is met:

1. The MTD is reached.
2. The OBD is found.
3. All of the dosing cohorts have been enrolled.

Protocol: 301OTC01

[REDACTED]

[REDACTED]

[REDACTED]

Possible dosing paths during dose [REDACTED]

[REDACTED]

[REDACTED]

[REDACTED]

[REDACTED]

[REDACTED]

[REDACTED] The protocol will also allow for adding an intermediate dose during either escalation or de-escalation, relative to the candidate doses outlined in

[REDACTED]

[REDACTED]

[REDACTED]

[REDACTED]

[REDACTED]

[REDACTED]

[REDACTED]

[REDACTED]

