Eligible subjects will receive a single peripheral intravenous (IV) infusion of DTX301. Three subjects will be enrolled in cohort 1 and a minimum of 2 to 3 subjects will be enrolled in each subsequent cohort; the number of subjects in each subsequent dosing cohort will be determined by subject results and availability of study drug. Subjects in cohorts 1 and 2 will be dosed at a minimum of 2 weeks (14 days) apart. The initial 3 subjects in cohort 3 will be dosed at a minimum of 1 week apart (7 days). Additional subjects to cohort 3 (cohort expansion) and subjects to cohort 4 (Dosing Process Optimization) may be dosed less than 1 week apart. Following the collection of a minimum of 12 weeks safety data, the data monitoring committee (DMC) will perform a review of a dosing cohort between the dosing of the last subject in one dosing cohort and the first subject in the next dosing cohort up to cohort 3. Dosing of additional subjects as expansion of cohort 3, and initiation of cohort 4 (Dosing Process Optimization) may occur in parallel, following the DMC review of a minimum of 12 weeks data from the initial 3 subjects in cohort 3. A continual reassessment method (CRM) will be used for dose finding to discover the OBD of DTX301. Cohort 4 is intended to dose at the OBD. Cohort 4 was prioritized in enrollment as OBD had been declared with cohort 3. Enrollment in cohort 4 was concluded after 2 patients enrolled as data on performance of prophylactic regimen, the focus of cohort 4, was evaluated and deemed sufficient.

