3.2.2. Definition of a Dose Limiting Toxicity

A dose limiting toxicity (DLT) is defined as any Adverse Event (AE), with a toxicity grade of three or higher ($AE \geq \text{Grade } 3$), that is considered related to the study drug by the investigator. As the N-CRM will be performed after 12 weeks of data have accrued for the last open cohort, only DLTs that occur within 12 weeks will be considered.

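### As the protocol and SAP are written, a non-fatal Grade 3–4 hyperammonemic crisis related to DTX301 is a DLT, yet requires neither an enrollment stop nor an ad hoc DMC review

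*Protocol*

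**What the plan says.** **Stopping criteria.** Enrollment stops for a death, a hepatic malignancy, or an event of Grade 3 or higher after DTX301. The Synopsis qualifies the last of these with "but excluding hyperammonemic crises, develops following administration of DTX301"; Section 3.2.7 has "but excluding hyperammonemic crises (Section 3.2.6), develops following administration of DTX301". Neither place limits the exclusion by cause or by grade. After a stop, restarting needs an approved substantial amendment (Protocol 3.2.7 and 9.3).

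**Ad hoc DMC review.** Protocol 9.3: "The DMC will meet on an ad hoc basis if an investigator reports an AE/SAE that meets any of the safety stopping criteria". The Synopsis and Sections 1.3.1 and 3.2.7 make the same link. Other extra meetings are allowed but not required. On scope, Section 1.3.1 adds: "The full scope of each review is outlined in the DMC charter".

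**DLT.** Protocol 10.5.1 counts any AE or SAE of at least "Grade 3 that is considered related to DTX301 by the investigator". SAP 3.2.2 counts any AE of Grade 3 or higher "that is considered related to the study drug by the investigator". Neither excludes crises. SAP 9.1 treats possible, probable and definite as related.

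**Dosing pace.** Minimum spacing is 14 days in Cohorts 1 and 2 and 7 days for the first three subjects of Cohort 3. After that, "Additional subjects to Cohort 3 (Cohort Expansion) and subjects to Cohort 4 (Dosing Process Optimization) may be dosed less than 1 week apart" (Protocol 1.3.1). SAP 3.1 records that "Enrollment in cohort 4 was concluded after 2 patients enrolled".

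**Corticosteroids.** The Protocol Introduction names high-dose corticosteroids among the circumstances in which adults with late-onset disease have become hyperammonemic. Sections 3.2.4 and 8.3.2 list steroid treatment as a time of raised metabolic demand. Section 8.2.4.1.2 starts prednisone at 60 mg/day, reactively in Cohorts 1–3 and prophylactically in Cohort 4. Relationship to the corticosteroid regimen is recorded for each AE (Protocol 9.1.4, SAP 9.1).

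**The concern.** Exempting an expected disease event from an automatic stop is reasonable, and that choice is not questioned here. The difficulty is that the exemption depends on the type of event and ignores attribution. A severe crisis that the investigator relates to the vector is serious enough to be a DLT, yet it requires less immediate oversight than an unrelated Grade 3 event of another kind, which stops enrollment and convenes the DMC. A severe crisis attributed only to the protocol's own prednisone falls outside both the DLT definition and the stopping criteria, although the protocol names the trigger.

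At stake is whether further subjects are given a single, irreversible dose after a severe treatment-related crisis before the DMC has looked at it. As written, that depends on someone choosing to convene the committee.

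**Working it through.** The plan gives no figure to reproduce on this point. The check is to read the definitions against each other and then to work out the timing.

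**Step 1. Apply the rules to each kind of event after DTX301.**

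| Event | DLT? | Stop required? | Ad hoc DMC meeting required? |
|---|---|---|---|
| Not a crisis, Grade ≥3, related | Yes | Yes | Yes |
| Not a crisis, Grade ≥3, unrelated | No | Yes | Yes |
| Crisis, fatal | If related | Yes (death) | Yes |
| Crisis, Grade 3–4, related to DTX301 | Yes | No | No |
| Crisis, Grade 3–4, prednisone only | No | No | No |
| Crisis, Grade 3–4, disease only | No | No | No |

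The prednisone-only row needs DTX301 to be rated unrelated, because a rating of possible already counts as related. The No entries concern the crisis itself. The laboratory pause in 3.2.7 applies to values that meet the same criteria. The text does not say whether a separately graded AE or ammonia value within a crisis would meet them on its own.

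**Step 2. Dosing ahead of scheduled review, at minimum spacing** (Protocol 1.3.1 and 9.3; Week 12 = 84 days).

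- Cohorts 1 and 2: subjects 2 and 3 on days 14 and 28 after the first dose. Review needs all three at Week 12: 2 × 14 + 84 = day 112 at the earliest.
- Initial Cohort 3: days 7 and 14. Review: 2 × 7 + 84 = day 98.
- Expansion and Cohort 4: at Amendment 5, 18 − 9 = 9 places remained (Protocol 3.2 and 15.3.5). Even at 7-day spacing they fill in (9 − 1) × 7 = 56 days, before the first of them reaches day 84. This is a planning-stage upper bound; Cohort 4 closed at 2.

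**Step 3. Scheduled reviews after the initial Cohort 3.** Protocol 9.3 has a Week 12 meeting for the first three Cohort 4 subjects. SAP Section 12 drops it, which leaves Week 52 as that cohort's only scheduled review. Section 9.3 times no meeting to the expansion subjects before Week 52.

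**Step 4. Steroid exposure** (Protocol 8.2.4.1.2). Cohort 4: at least 5 + 28 = 33 days at 60 mg/day, then a taper of 6 × 5 = 30 days. Reactive regimen in Cohorts 1–3: 4 weeks at 30–60 mg/day before the weekly taper.

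**The case against.** The strongest reply is that stopping rules and DLTs serve different purposes. An event expected from the disease should not halt a trial automatically, but a related case should still inform dose finding. That stands, and it is why no automatic stop is proposed.

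Much else stands too:

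- The DMC may recommend a pause at any time (9.3).
- A crisis leading to hospitalization is an SAE (9.1.1.2), and an SAE related to DTX301 is handled as a SUSAR (9.1.2.2.1).
- Spot ammonia is taken about weekly through Week 12 (3.2.3.1).
- Clinical and metabolic stability is required before steroids (8.2.4.1.1 and 8.2.4.1.2).
- A Week 12 review precedes each escalation.
- The unseen charter may contain further triggers.

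These safeguards show that a crisis would be noticed and could be reviewed. They do not make review mandatory, and SUSAR handling does not reach a prednisone-only crisis.

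Three stronger readings are tempting and not supported:

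- *Such a crisis escapes reporting altogether.* The SAE and SUSAR provisions contradict this for hospitalized or otherwise serious cases.
- *The protocol forecasts steroid-induced crises.* It names a trigger and gives contingency guidance. Section 1.3.1 reports no SAE with DTX301 to date.
- *One such DLT would redirect dose finding.* Take the SAP 3.2.7 prior (alpha mean −2.3097, SD 1.6604; log-beta fixed at −0.4323 because its SD is 0.0044; reference 6×10¹²). One DLT among three Cohort 1 subjects gives posterior mean p(DLT) of 0.188, 0.296 and 0.354 at the three doses. The dose nearest 0.25 is 6×10¹². With no DLT the nearest is 1×10¹³, but SAP 3.2.5 allows only one level up, so the next dose is again 6×10¹². One DLT after two cohorts (0.101, 0.176, 0.222) or three (0.064, 0.118, 0.153) still selects 1×10¹³. Under the SAP rule, a single DLT does not change the next dose in the planned cohorts.

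The model does not fill the gap either: it recommends no safety stop before two DLTs (SAP 3.2.8).

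**Conclusion.** The point holds on the protocol and SAP text. A non-fatal Grade 3–4 crisis related to DTX301 is a DLT with no required stop and no required ad hoc DMC review for the crisis itself. One attributed only to the protocol's prednisone requires neither and is not a DLT.

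The size is the number of subjects who can be dosed before a required review: two more in each of the first three cohorts, and at the planning stage up to eight more after the first across the expansion and Cohort 4. How often this would matter cannot be estimated, because the documents contain no crisis rate.

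The conclusion assumes that the charter adds no such trigger and that AEs or ammonia values within a crisis are not treated as separate qualifying events. With Cohort 4 closed at 2 subjects, the practical benefit is to any further dosing under this protocol. It is a cheap improvement in oversight, with no evidence of harm behind it.

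**What to change.** Add to Protocol 3.2.7, its Synopsis copy and 9.3, and mirror in SAP Section 10:

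> Any Grade ≥3 hyperammonemic crisis assessed as possibly, probably or definitely related to DTX301 or to the corticosteroid regimen will be reported within 24 hours and reviewed by the DMC ad hoc before the next subject is dosed. Such a crisis does not by itself meet the stopping criteria or require a substantial amendment to continue. Crises attributed only to the underlying disease or another non-study cause remain exempt.

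Tying the review to the next dosing is essential. A referral without a deadline would achieve little where subjects may be dosed less than a week apart.

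The DLT definition and the N-CRM stay as they are, and both attributions are already collected. The cost is a short paragraph, a matching entry in the SAP, an occasional ad hoc DMC review and a short delay to the next dosing.

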1.1 Adeno-Associated Viral Vectors

Adeno-associated virus (AAV) is a nonenveloped, icosahedral, single-stranded DNA virus. Given that wild-type AAV displays wide tissue tropism and is capable of persisting in tissues for long durations without pathogenic effects, the use of recombinant AAV vectors has become a popular tool for gene delivery. Additionally, recombinant AAV vectors are nonreplicating and the vector genomes exist as an episome following tissue transduction, minimizing the risk of insertional mutagenesis [Nakai 2001]. Since the first genetic engineering of wild-type AAV as a gene delivery vector in the early 1980s, recombinant AAV has shown great promise as an effective and safe gene delivery vehicle for treatment of diseases [Gao 2005].

Adeno-associated virus serotype 2 (AAV2) was the first AAV that was used for gene transfer applications and has been used in numerous studies for a variety of diseases such as alpha 1-antitrypsin deficiency, Batten disease, and cystic fibrosis [Mingozzi 2011]. In animal models, AAV-mediated gene transfer was shown to treat the underlying disease for many years [Snyder 1999; Mount 2002; Wang 2005; Nichols 2010]. However, in humans, AAV2-mediated delivery was either sub-therapeutic or only lasted a few months [Manno 2003; Manno 2006]. This was attributed to several limitations of AAV2 vectors including low transduction efficiency [Yan 2002], high seroprevalence of neutralizing antibodies against AAV2 in humans [Boutin 2010], and potentially destructive T-cell responses to capsids [Gao 2009; Vandenberghe 2006; Wang 2007]. Additionally, there has been evidence of B-cell responses against the transgene product in an animal model of hemophilia [Herzog 2001].

